2.3 EXPLORATORY OBJECTIVES

The exploratory objectives for this study include subgroup analyses of the primary efficacy outcome variable as defined by age (<65 vs. \geq 65), pre-treatment NIHSS score (0–2 vs. 3–5), last known well time to treatment (0–2 hours vs. >2–3 hours), and stroke subgroups (RISS vs. non-RISS), respectively.

The following endpoints will also be explored:

- NIHSS
- BI
- GOS
- Stroke recurrence (based on AE monitoring) within 90 days
- Cognition and behavior (modified 30-minute battery: Controlled Oral Word Association test; Hopkins Verbal Learning Test-Revised [HVLT-R] trials 1, 2, and 3; digit symbol coding from the Wechsler Adult Intelligence Scale III [WAIS III]; Forward and Backward Digit Span test; Benton Judgment of Line Orientation test, form V; HVLT-R trial 4 and recognition; semantic fluency [Animal Naming test]; Boston Naming Test [BNT; 15-item short form]) at Day 90
- Ambulatory performance (as measured by walking speed) at Day 90
- Center for Epidemiologic Studies-Depression (CES-D)
- Quality of life (European Quality of Life [EQ-5D] questionnaire) at Day 90
- Stroke Impact Scale-16 (SIS-16) at Day 90

3. STUDY DESIGN

3.1 DESCRIPTION OF STUDY

PRISMS is a double-blind, multicenter, randomized, Phase IIIb study to evaluate the efficacy and safety of IV alteplase in AIS patients with mild strokes that do not appear to be clearly disabling. The trial will consist of a screening assessment, randomization, and treatment followed by a Day 5 visit, 30-day phone call, and a 90-day follow-up visit. Treatment should start within 3 hours from last known well time (stroke symptom onset).

Screening assessments will be used to determine the eligibility of the patient. Patients meeting eligibility criteria will be randomized in a 1:1 ratio to receive either:

1. One dose of alteplase 0.9 mg/kg IV (not to exceed 90 mg) and one dose of oral aspirin placebo, OR

[figure not shown]
Alteplase—Genentech, Inc.
25/Protocol ML29093, Version 3

2. One dose of IV alteplase placebo and one dose of oral aspirin 325 mg (Figure 1).

Every effort should be made to ensure both study drugs are initiated within 3 hours of last known well time. If institutional policies on oral medications make it challenging to administer the oral aspirin/aspirin placebo within 3 hours of last known well time, the oral study drug may be given up to 24 hours after the last known well time. IV alteplase/IV alteplase placebo MAY NOT be initiated beyond 3 hours of last known well time under any circumstances.

A full schedule of assessments is provided in [Appendix 1](#).

Figure 1 Abbreviated Study Schema

ASA = aspirin; CT = computed tomography; IV = intravenous; MRI = magnetic resonance imaging; mRS = modified Rankin Scale; NIHSS = National Institutes of Health Stroke Scale.

Due to the emergency nature of randomization in acute stroke clinical trials, treatment assignments must be made in an expeditious manner that also ensures even distribution in the treatment groups. A “step forward” randomization regimen stratified by site will be used to ensure that a randomized treatment assignment is available upon patients’ arrival at the hospital and treatment can initiate immediately upon signing informed consent and eligibility confirmation. Further details on step forward randomization can be found in Section 4.2, Method of Treatment Assignment and Blinding.

An independent Data Monitoring Committee (iDMC) will provide ongoing review of potential safety concerns and review efficacy and safety outcomes to inform a futility interim analysis after 50% of patients have achieved the primary endpoint (following completion of the Day 90 visit). The composition of the iDMC and analysis will be documented in detail in a separate iDMC charter.

Alteplase—Genentech, Inc.
26/Protocol ML29093, Version 3

3.2 LENGTH OF STUDY

Based on study enrollment projections, this study is estimated to take approximately 4 years to complete, from first patient in to last patient's last visit (LPLV), when the final patient completes the 90-day follow-up.

3.3 END OF STUDY

The end of the study is defined as the date when the LPLV occurs. The LPLV is expected to occur approximately 90 days (\pm 14 days) after the last patient is enrolled into the study.

3.3.1 Number of Patients

Approximately 948 patients with AIS and mild strokes will be enrolled in the study across 75 sites in North America.

3.4 RATIONALE FOR STUDY DESIGN

This study is designed to assess whether alteplase administered within 3 hours of last known well time is superior to standard of care (i.e., aspirin) in patients with mild stroke. Patients will be randomized 1:1 to receive either IV alteplase plus aspirin placebo or IV alteplase placebo plus aspirin 325 mg; hence, this is an active-comparator trial. Other than the study intervention, patients will receive standard of care for AIS at the enrolling institutions. The primary endpoint using the mRS assessment of global disability at 90 days is standard for current AIS trials.

The study design of PRISMS has the following characteristics:

- **Consistent with the currently approved indication in the alteplase USPI:** Treatment with alteplase in PRISMS will occur in otherwise eligible AIS patients within 3 hours from the last known well time.
- **Conduct of a large, multicenter study:** The Sponsor plans to enroll 948 patients across approximately 75 sites in North America. (For comparison, the two NINDS trials enrolled a total of 624 patients.)
- **Multiple endpoints involving different events:** In addition to the primary efficacy endpoint of mRS at Day 90, which measures disability, secondary endpoints at Day 90 will include an ordinal mRS assessment and global favorable recovery, as calculated using the Global Outcome Measure derived from the mRS, NIHSS, BI, and GOS.

3.4.1 Rationale for Alteplase Dosage

The dose selected for alteplase (0.9 mg/kg, maximum 90 mg) is the approved dose for eligible patients with AIS in North America and is considered the standard of care by the stroke community ([Jauch et al. 2013](#)).

3.4.2 Rationale for Patient Population

The patients for this trial will be recruited from all AIS patients presenting to Emergency Departments in whom treatment can be initiated within 3 hours of last known well time at approximately 75 clinical sites within North America. As described in Section 1.3, eligible patients with mild stroke will be enrolled in this study. Currently, the alteplase USPI warns against the use of alteplase in patients with “minor neurologic deficit and rapidly improving stroke symptoms” due to lack of data. Retrospective and observational data suggest potential benefit of alteplase in these patients, with a favorable benefit-risk profile.

The definition of mild stroke for PRISMS is an NIHSS score ≤ 5 and not clearly disabling. This includes patients whose symptoms are persistently mild as well as those with RISS.

An NIHSS score ≤ 5 was chosen as one criterion in the definition of mild stroke for PRISMS for the following reasons:

1. An NIHSS score ≤ 5 is commonly used as an exclusion criterion for many current AIS studies, suggesting that these patients are underrepresented in current stroke research and are treated differently by the stroke community, as shown in [Table 2](#).
2. The largest retrospective analysis of mild stroke from the Get With the Guidelines® registry included 29,200 stroke patients who did not receive alteplase due to mild or improving symptoms. This analysis found that 80.1% of patients with mild or rapidly improving stroke who did not receive alteplase (and had a recorded NIHSS score) had an initial NIHSS score ≤ 5 ([Smith et al. 2011](#)).

Based on these findings, an NIHSS score ≤ 5 was determined to be the most appropriate cut-off to define the patient population with mild stroke.

Table 2 NIHSS Exclusion Criteria of Recently Completed and Ongoing Acute Ischemic Stroke Trials

Recently Completed AIS Trials	Exclusion	Ongoing AIS Trials	Exclusion
Combined Approach to Lysis Utilizing Eptifibatide and rt-PA in Acute Ischemic Stroke (CLEAR Stroke) Trial	NIHSS≤5	ARTSS	NIHSS≤9
Intravenous Thrombolysis Plus Hypothermia for Acute Treatment of Ischemic Stroke	NIHSS≤6	SHINE	NIHSS<3
Albumin in Acute Ischemic Stroke Trial (ALIAS) Part One	NIHSS≤5	The Intravascular Cooling in the Treatment of Stroke 2/3 (ICTuS 2/3) Trial (ICTuS2/3)	NIHSS≤6
Study of the Combination Therapy of rt-PA and Eptifibatide to Treat Acute Ischemic Stroke (CLEAR-ER)	NIHSS≤5	Safety/Feasibility of Autologous Mononuclear Bone Marrow Cells in Stroke Patients	NIHSS≤5
Albumin in Acute Ischemic Stroke Trial (ALIAS) Part Two	NIHSS≤5	SWIFT PRIME	NIHSS≤7
Mechanical Retrieval and Recanalization of Stroke Clots Using Embolectomy (MR RESCUE)	NIHSS≤5	PENUMBRA THERAPY	NIHSS≤7
NeuroThera Efficacy and Safety Trial-3 (NEST3)	NIHSS≤6	PENUMBRA 3D	NIHSS≤7
		CLOTBUST-ER	NIHSS≤9

AIS=acute ischemic stroke; NIHSS=National Institutes of Health Stroke Scale.

Source: www.clinicaltrials.gov. Accessed August 2013. Note that the NIHSS criteria for the trials listed are mentioned in the inclusion criteria, whereas the entries in the above table were adapted to list the corresponding exclusion criteria.

It is notable that the alteplase USPI (2011) distinguishes patients with minor neurological deficit from those with RISS. However, PRISMS combines these two patient groups into one operationally defined patient population (mild stroke): all eligible patients with an NIHSS score≤5 at the time of randomization without clearly disabling symptoms, irrespective of previous NIHSS scores. Data demonstrating low alteplase use in patients with NIHSS scores≤5 do not distinguish between whether the patient's deficit was persistently mild or improved to this status (Smith et al. 2011). Furthermore, no data exist that suggest patients who improved to a mild status at the time of treatment with alteplase have different outcomes from patients whose neurologic deficit is persistently mild. To date, available data suggest that alteplase therapy would potentially be beneficial in both patients with RISS who improve to an NIHSS score≤5 and patients with persistently mild deficits with an NIHSS score≤5.

Alteplase—Genentech, Inc.
29/Protocol ML29093, Version 3

Conversely, patients who improve to an NIHSS score > 5 at the time of treatment decision will be excluded from PRISMS as they are not considered to have RISS. Current clinical practice suggests that these patients would still have a moderate or severe stroke at the time of treatment decision and should receive alteplase, if eligible, rather than be randomized to a study. Such patients should not be defined as rapidly improving, given that they have not improved to an NIHSS score low enough to merit withholding therapy. This definition of RISS is consistent with a recent consensus statement by leading stroke and emergency medicine experts (Levine et al. 2013).

PRISMS will also exclude patients who are assessed at the time of pre-treatment to be clearly disabled. These clearly disabling deficits at presentation may include, but are not limited to, homonymous hemianopsia, severe limb weakness, severe aphasia, hemineglect, or cortical blindness. Patients with clearly disabling deficits will be excluded from this study irrespective of the NIHSS score at time of randomization, as current clinical practice and ethical responsibility suggest that these patients should be evaluated to receive alteplase rather than be enrolled in a randomized study where they may receive alteplase placebo.

3.4.3 Rationale for Control Group

The overall rationale for this trial is to determine whether IV alteplase improves outcomes in patients with mild stroke. The control group (i.e., mild stroke patients who receive standard of care) has been included so that outcomes in the active treatment group can be compared to those who receive standard of care. The control group will receive IV alteplase placebo and 325 mg of oral aspirin. The rationale for the control group receiving aspirin is that it would be unethical to withhold a dose of aspirin from patients who would not be receiving active study drug. The standard of care for patients suffering from AIS who are ineligible for IV alteplase therapy is oral aspirin administered within the first 24 hours after the onset of their stroke symptoms.

3.5 OUTCOME MEASURES

3.5.1 Efficacy Outcome Measures

The primary efficacy outcome measure for this study is:

- A favorable functional outcome, defined by an mRS score of 0 or 1 at Day 90 post-randomization
 - All mRS assessments will be made by investigators blinded to treatment assignment who are trained and certified in mRS administration.

The secondary efficacy outcomes are measured at Day 90 and listed below:

- Ordinal mRS
- Global favorable recovery (Global Outcome Measure derived from mRS 0 – 1, NIHSS 0 – 1, BI \geq 95, and GOS = 1)

Alteplase—Genentech, Inc.
30/Protocol ML29093, Version 3

3.5.2 Safety Outcome Measures

The safety outcome measures for this study are as follows:

- Incidence of sICH within 36 hours (primary safety assessment)
sICH is defined as any neurological decline attributed to new ICH seen on imaging by the investigator. New ICH seen on imaging will be later confirmed on independent reading by blinded central study radiologists.
- Any ICH within 36 hours
- Overall mortality within 90 days
- Stroke-related and neurological deaths within 90 days
- Incidence, severity, and spectrum of all AEs and SAEs

Symptomatic Intracranial Hemorrhage

In this study, an ICH is considered symptomatic if it is not seen on computed tomography (CT) or magnetic resonance imaging (MRI) scan at baseline and any neurologic decline is attributed to it by the local investigator. To detect intracranial hemorrhage, neuroimaging (CT or MRI) scan is required at 22 to 36 hours. Additional neuroimaging should be performed at any time based on the investigator's discretion that clinical findings suggested hemorrhage. Details on MRI types are described in Section 4.5.1.6.

Intracranial hemorrhage events will include classifications of intracerebral hemorrhage (hemorrhagic infarct type 1 or type 2, parenchymal hematoma type 1 or type 2, or remote intraparenchymal hemorrhage type 1 or type 2). Descriptions of each type of intracerebral hemorrhage are shown in the table below. Additionally, subarachnoid hemorrhage, subdural hemorrhage, or epidural hemorrhage should be noted.

Table 3 Intracerebral Hemorrhage Definitions

Type	Description
HI type 1	Small petechiae along margin of infarct
HI type 2	More confluent petechiae within the infarcted area but without space-occupying effect
PH type 1	Hematoma in $\leq 30\%$ of the infarcted area with some slight space-occupying effect
PH type 2	Dense hematoma $> 30\%$ total of the infarcted area with substantial space-occupying effect or any hemorrhagic area outside the infarcted area
rPH type 1	Small or medium sized blood clots located remote from the actual infarct; a mild space-occupying effect could be present. Remote primary intracerebral hemorrhage
rPH type 2	Large confluent dense blood clots in an area remote from the actual infarct; substantial space-occupying effect might be present.

HI=hemorrhagic infarct; PH=parenchymal hematoma; rPH=remote parenchymal hematoma.

Source: [Wahlgren et al. 2007](#).

Alteplase—Genentech, Inc.
31/Protocol ML29093, Version 3

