In the case when pre-mixed IV drug is not used (e.g., patient is determined to be ineligible for study or declines informed consent prior to drug administration), sites will enter drug kit IDs into IWRS and indicate that the kits were not used. IWRS will then assign a new set of drug kit IDs for the pharmacist to label with “Use Next” labels. The pharmacist will properly dispose of the pre-mixed IV drug and the matching aspirin/aspirin-placebo kit in accordance with institutional guidelines.

Prior to the first patient enrolled at a site, a site will register with IWRS as part of site activation, which will assign drug kit IDs ahead of time for the first potential patient. Once the first patient is enrolled at a site, the procedure described above will commence.

Study Unblinding

If a clinical situation arises in which the investigator thinks it is necessary to unblind in the interest of patient safety, the Medical Monitor must be notified immediately to discuss the intended unblinding. Unblinding should occur only in settings where identification of the study treatment is critical for treatment decisions. IWRS will be used for the unblinding process. All unblinded patients will remain in the study and require all follow-up visits.

Treatment codes should not be broken except under circumstances deemed necessary by the site investigator. The investigator should document and provide an explanation for any premature unblinding (e.g., unblinding due to sICH or severe systemic bleeding that requires blood products if IV alteplase was administered, or unblinding due to clinical worsening during the IV alteplase time window that would lead to IV alteplase administration if not already given).

For regulatory reporting purposes, and if required by local health authorities, the Sponsor will break the treatment code for all serious, unexpected suspected adverse reactions (see Section 5.7) that are considered by the investigator or Sponsor to be related to study drug.

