4.5.1.6 Other Disease-Specific Assessments

Neuroimaging may consist of a non-contrast CT or MRI of the brain. If an MRI is used in the acute setting (to determine study eligibility), it must include the following at a minimum: (1) DW MRI, (2) either susceptibility-weighted (SW) imaging or gradient echo (GRE) sequences, and (3) FLAIR sequences.

Non-contrast CT or MRI will be performed at baseline to ensure that the patient does not have evidence of acute ICH prior to study drug administration.

An additional non-contrast CT or MRI will be performed at 22 to 36 hours from the initiation (bolus) of study drug infusion. The purpose of this is to evaluate for ICH in the patient. An NIHSS should be performed at the time this CT scan or MRI is performed, but prior to reviewing imaging results to avoid biasing the assessment. If an MRI is performed, in addition to the above requirements for the baseline visit MRI, it must also include T1 and T2 sequences.

Alteplase—Genentech, Inc.
40/Protocol ML29093, Version 3

Additional CT scans or MRIs should be performed based on the investigator's discretion, or if any clinical findings suggest ICH (such as new headache, nausea, vomiting, significant deterioration of neurological status, or rapid increase of blood pressure). If an ICH is identified, the NIHSS score should be reassessed at the time and recorded on the Adverse Event eCRF.

CT scans or MRIs performed at baseline, between 22 to 36 hours, and additional imaging performed due to clinical suspicion of deterioration up until 36 hours after study drug administration, will be evaluated by a central team of radiologists blinded to the clinical attributes of the case. These images will need to be sent to the central radiologists by the local site.

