4.7.2 Study Treatment Discontinuation

The study intervention should be discontinued if the patient displays symptoms concerning sICH during the infusion of the study drug. Prompt imaging should be done to assess for ICH. If ICH is seen, study drug infusion should not be resumed and the treatment assignment may be unblinded if blood products (to reverse the biological activity of IV alteplase) are indicated. If ICH is not seen, study drug infusion should immediately be restarted *in order to complete the infusion within 4 hours after the last known well time at the same rate as the previous infusion until the remainder of study drug is infused.*

Patients must discontinue study treatment if they experience any of the following:

- Anaphylactoid reaction (including angioedema)
- Serious bleeding (not controllable by local pressure) at puncture site or serious bleeding in a critical location (e.g., intracranial, gastrointestinal, retroperitoneal, pericardial)

The primary reason for study treatment discontinuation should be documented on the appropriate eCRF. Patients who discontinue study treatment prematurely will not be replaced. Patients who discontinue study treatment prematurely will continue in the study and be followed through Day 90, based on the intent-to-treat (ITT) principle.

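### Whether a hemorrhage counts as symptomatic is one local judgment that may be made after the treatment code is broken, and the protocol neither orders nor blinds it

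*Protocol*

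**What the plan says.** All references are to the current protocol text, Version 3.

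- **Endpoint.** Section 3.5.2 lists "Incidence of sICH within 36 hours (primary safety assessment") first among the safety outcomes. An ICH absent at baseline is symptomatic if "any neurologic decline is attributed to it by the local investigator". Appendix 13 repeats this definition. No minimum change in NIHSS is set.
- **Central reading.** Section 3.5.2 adds: "New ICH seen on imaging will be later confirmed on independent reading by blinded central study radiologists". Section 4.5.1.6 says the scans "will be evaluated by a central team of radiologists blinded to the clinical attributes of the case".
- **Code breaks.** Section 4.2 leaves the need for a break to the site investigator. It limits breaks to cases where knowing the treatment is critical for a treatment decision, and the Medical Monitor must be told at once. One example given is "unblinding due to sICH or severe systemic bleeding that requires blood products if IV alteplase was administered". Section 4.7.2, on ICH seen after the infusion is stopped for suspicious symptoms, says "the treatment assignment may be unblinded if blood products (to reverse the biological activity of IV alteplase) are indicated". Unblinded patients stay in the study.
- **NIHSS.** Section 4.5.1.6 places the 22 to 36 hour NIHSS "prior to reviewing imaging results to avoid biasing the assessment" and requires a repeat score when an ICH is found. Appendix 1, note i, requires a score when clinical findings suggest ICH.
- **Blinded raters.** Section 3.5.1 states: "All mRS assessments will be made by investigators blinded to treatment assignment". It has no such sentence for NIHSS, Barthel Index or Glasgow Outcome Scale, the other three components of the global outcome.

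**The concern.** The endpoint has two parts: blood on the scan, and decline attributed to that blood. Blinded central reading protects the first. The second rests on one person at the site, and the central readers cannot check it because they do not see the clinical picture.

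That same person may learn the assignment because of the hemorrhage in question. An investigator who knows that alteplase was given has a reason to put an uncertain decline down to the bleed. One who knows that aspirin was given has a reason to call it progression of the infarct. Either tendency would enlarge the sICH difference between arms.

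The protocol guards against the same kind of bias elsewhere: the Visit 2 NIHSS is scored before the scan is reviewed, and the mRS rater is blinded. The attribution has neither safeguard. What is at stake is the sICH difference, which the benefit-risk argument in Section 1.3 and Table 1 turns into a number needed to harm of 50.

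**Working it through.** The protocol states no figure for this point, so there is none to reproduce. The check has two parts.

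**1. Is the attribution protected anywhere in the text?**

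| Step | Recorded or checked? | Protected from knowledge of treatment? |
|---|---|---|
| New blood on the scan | Yes, central reading (3.5.2, 4.5.1.6) | Yes, blinded readers |
| NIHSS when findings suggest ICH | Yes (Appendix 1, note i) | In practice yes for a break prompted by a scan, since the score comes at the time of the findings |
| NIHSS when ICH is identified | Yes (4.5.1.6) | No order relative to a break is stated |
| Yes/no attribution of decline to the ICH | Local judgment only (3.5.2, Appendix 13) | No: not ordered before a break, not assigned to a blinded person, not adjudicated |

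The gap is the last row. The trigger in Section 4.7.2 is ICH being seen with blood products indicated, so a break there does not require the bleed to have been classified as symptomatic first. The example in Section 4.2 does speak of sICH, which suggests that a working judgment often precedes the break, but nothing requires it to be recorded.

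**2. How few classifications would matter?**

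Inputs:
- assumed sICH rates of 2% with alteplase and 0% with control (Section 1.3);
- 948 patients (Section 6.1) randomized 1:1 (Section 3.1), so 948 / 2 = 474 per arm;
- Fisher's exact test (Section 6.3).

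Expected events are 0.02 × 474 = 9.48 with alteplase and 0 × 474 = 0 with control.

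Two-sided Fisher p for event counts out of 474 per arm:

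| Alteplase | Control | p |
|---|---|---|
| 9 | 0 | 0.0038 |
| 9 | 1 | 0.0208 |
| 9 | 2 | 0.0639 |
| 8 | 1 | 0.0382 |
| 7 | 1 | 0.0692 |
| 8 | 2 | 0.1075 |
| 6 | 0 | 0.0308 |
| 5 | 0 | 0.0618 |

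The answer depends on the pattern. From 9 versus 0, two more control events pass 0.05. One fewer with alteplase plus one more with control (8 versus 1) does not. Without any control events, four alteplase events must be lost (5 versus 0) before p exceeds 0.05. From 9 versus 1, two changes are enough (7 versus 1, or 8 versus 2).

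These rows show sensitivity only. The protocol gives no figure for how many codes would be broken or how many attributions would change.

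**The case against.** The strongest reply has four parts.

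- **Safeguards exist.** NIHSS must be scored when findings suggest ICH and again when ICH is identified, so the decline itself is documented. This stands, and it removes any claim that decline goes unrecorded. It does not settle the attribution, which is a separate judgment.
- **Exposure is small and the cases are clear.** Breaks are limited to situations where treatment identity is critical or blood products are indicated, and the Medical Monitor is involved. Bleeds serious enough for that may leave little doubt about symptoms. This largely stands: only some ICH cases are exposed, and perhaps the least equivocal ones.
- **The tests are exploratory.** Section 6.3 says so and adjusts no alpha, so crossing 0.05 decides nothing formally. This stands. The estimate still informs the benefit-risk judgment.
- **The definition is deliberate.** Section 1.3 says that it follows the definition of the pivotal NINDS trial. This stands, and the lack of an NIHSS threshold is not criticized here.

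On the raters, the trial is double-blind and Section 6.2 treats the global outcome as supportive, so that part concerns only the few unblinded patients.

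Two stronger readings are tempting. A reader might infer that the sICH difference will be biased, or that two or three altered attributions would always overturn the result. The protocol allows a break before the attribution but does not prescribe that order, it gives no number of breaks, and the 8 versus 1 row contradicts the second inference. A reader might also infer that only attributions made before a break should count. That could drop the most urgent bleeds from the primary safety count and understate harm.

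**Conclusion.** The point holds in a limited form. The symptomatic component of the primary safety outcome is a local judgment without independent confirmation, and it can be made with treatment known.

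The likely direction of bias is away from zero. This rests on the assumption that knowing the treatment influences uncertain attributions in the expected way. The size is unknown, because it depends on how many ICH cases have a code break before the attribution and how many of those are uncertain. The table above applies only if the assumed 2% and 0% and 474 per arm hold.

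The missing blinded-rater rule for three of the four global components is a smaller gap of the same kind. Both are worth closing because closing them is cheap, not because the results are shown to be at serious risk.

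**What to change.** - **Sections 3.5.2 and 4.2.** When ICH is seen, the investigator records a yes/no attribution of decline, with date and time, before requesting the code through IWRS, wherever this does not delay care. If the break comes first, the attribution is flagged as made after unblinding.
- **Counting rule.** Every sICH case, flagged or not, stays in the primary sICH count. A sensitivity analysis reclassifies the flagged cases, for example all as symptomatic and then all as not symptomatic.
- **Section 3.5.1.** Extend the blinded-rater sentence to Day 90 NIHSS, Barthel Index and Glasgow Outcome Scale.

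The clinical rule on when a code may be broken is unchanged. The cost is one time-stamped eCRF field with its flag, a few sentences of text, brief documentation at the time of the event, and scheduling a blinded rater certified as needed for these scales. The last item is not entirely free: Appendices 7 and 8 require separate certification for NIHSS and mRS, and Appendix 1, note j, allows the mRS by telephone, so one person at one visit cannot be assumed.
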